6.3.8 Post-Pregnancy follow-up

Pregnancy outcome will be obtained via clinic visit, telephone contact or from HFEA database review for subjects who were pregnant as of their most recent vaginal ultrasound (5-8 gestational weeks or additional ultrasound if post-5-8 gestational weeks), and a **Post-Pregnancy Follow-up** eCRF.

6.3.9 Additional Ultrasound > 8 weeks (Optional)

Any additional vaginal ultrasounds performed after 8 weeks may be recorded on an **Additional Ultrasound** eCRF. The collection of this data is optional, however encouraged.

Data will include the following:

- Date of ultrasound
- Result of initial pregnancy ultrasound
 - Number of fetal sacs and number of fetal heartbeats

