5.1 Overall Trial Design and Plan

In general, the Eeva EU/Canadian trial will include 22 investigational sites. Each site will conduct the trial using the same clinical protocol.

Recruitment of patients at each site, with subjects who voluntarily consent to participate, is expected to continue for up to 9 months. Additional follow-up after embryo transfer will take place up to Day 12-18 days to verify biochemical pregnancy and at 5-8 gestational weeks to verify clinical pregnancy. Additionally, pregnancy outcomes will be collected via eCRF for subjects who were pregnant at the 5-8 week gestational follow-up visit (or subsequent ultrasound results). Total duration of the trial, including start up and close out activities, is approximately 19 months. Desired follow-up endpoints and additional collection of outcomes like spontaneous miscarriage is not being considered in the timeline for completion.

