6.1 Endpoints

Primary Endpoint: Implantation rate from embryo transfers performed on day 3 or day 5.

Secondary Endpoints: Utilization rate, Clinical pregnancy rate, Ongoing pregnancy rate, Multiple pregnancy rate, Spontaneous miscarriage rate.

Endpoints are defined as follows :

- Implantation rate (number of sacs with fetal heart beat/ total number of embryos transferred)
- Utilization rate (transferred + frozen/ fertilized eggs) X100.
- Clinical pregnancy rate (at approximately 5-8 weeks gestational age)
- Multiple pregnancy rate defined as a clinical pregnancy with ≥ 2 fetal sacs.
- Spontaneous miscarriage rate as a desired follow-up endpoint.

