6.4.1.2 Definition of the reporting period for safety surveillance

The reporting period for safety surveillance begins when the subject is included into the trial (date of first signature of informed consent) and continues after ET until achievement of implantation and (confirmation of) pregnancy. There is no pregnancy follow-up planned in the frame of this study.

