7.4.2 Secondary Endpoint(s)

The secondary endpoints are:

- Clinical Pregnancy (assessed by ultrasonography at weeks 5 to 8)
- Ongoing pregnancy rate (assessed by ultrasonography at weeks 10 to12)
- Multiple pregnancy rate (assessed by ultrasonography at weeks 5 to 8)
- Utilization Rate ([number of transferred and frozen embryos divided by number of normally fertilized oocytes] x100)
- Spontaneous miscarriage (communicated during medical appointment or by telephone contact).

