- Is disclosed to Institution, its employees, agents, subcontractors or affiliates after acceptance of this protocol by a third party who has a right to make such disclosure in a non-confidential manner; or
- Is or becomes part of the public domain through no fault of the Institution, its employees, agents, subcontractors or affiliates.
- Nothing in this trial will be construed to restrict the Institution or Investigator from disclosing confidential information as required by law or court order or other regulatory order or request,

provided in each case the party requested to make such disclosure will timely inform Merck KGaA and use all reasonable efforts to limit the disclosure and maintain the confidentiality of such confidential information to the extent possible. In addition, the disclosing party will permit Merck KGaA to attempt to limit such disclosure by appropriate legal means.

- Further, during the term of this protocol and thereafter, the Institution, its employees, agents, subcontractors or affiliates will not use the confidential information for any purpose other than that indicated in this protocol and the clinical research agreement without Merck KGaA's prior written approval.
- Institution, its employees, agents, subcontractors or affiliates will not disclose to Merck KGaA any information which is confidential or proprietary to a third party unless Institution has first obtained the prior written approval of both such third party and Merck KGaA.

11 Trial or site Discontinuation

The Sponsor may temporarily or permanently discontinue the trial at a single site or at all sites for ethical, compliance or other reasons. If this is necessary, the Sponsor will endeavor to provide advance notification to the site. If the site or trial is suspended or discontinued, the Investigator will be responsible for ensuring prompt notification to the EC/IRB. Where required by local regulations, the Sponsor will be responsible for informing the EC/IRB of trial or site discontinuation.

12 Trial Closure

Upon completion (when all subjects enrolled have completed the 5-8 weeks Ultrasound or Clinical Pregnancy data collection requirements or have previously exited the trial, and the eCRFs and queries have been completed) or termination of the trial, Merck KGaA will notify the sites.

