14.6 Exploratory Variables

Multiple Linear regression analysis of IR (based on subject level) as dependent variable and treatment as independent parameter effected by the following confounding factors

Factors	Description
Stimulation protocol	Categorical variable, 3 states: Agonist Luteal phase; Antagonist; and Agonist Mirco-dose Flare and Other
Drugs used	Categorical variable, 3 states: recombinant Gn, urinary Gn, and mix-use of recombinant and urinary Gns
Day of transfer	Categorical variable, 2 states: D3 Vs D5/6
Age of patients	Continuous variable , years
Culture medium	Categorical variable, 5 states: Quinn's Advanced Fertilization, Global Medium, Vitro life G-IVF, Irvine Single Step Medium, and Other

A better estimate of implantation rate will be obtained based on subject level adjusted for confounding factors by a Multiple Linear regression.

Given the exploratory nature of the design, the model will be investigated stepwise and repeated backward. The final model will exclude backward P-values > 0.10.

The Center effect will also to be considered in the model.

The results of regression analysis will be reported with the following items

- Regression Coefficient with 95% CI
- Standard Error
- P-value
- Coefficient of Determination (R^2)

Subgroup analyses

Further subgroup analysis based on selected baseline parameter could be conducted as follows.

- 1) IR of the two treatment groups at each site (descriptive summary statistics with 95% CI,

and RR with 95% CI and P value). The Risk Ratio, 95% CI and P-value will be calculated, provided the number of subjects in a site will be at least 30, otherwise only descriptive statistics will be provided for that particular site.

- 2) IR, CPR, OPR and SMR of the two treatment groups for subgroups of patients with ET on D3 and D5/6 (descriptive summary statistics, RR with 95% CI and P value);
- 3) IR, CPR, OPR and SMR of the two treatment groups for subgroups of patients with age ≤35 and >35(descriptive summary statistics, RR with 95% CI and P value).
- 4) IR of the two treatment groups for subgroups of patients using 5 types of culture media (descriptive summary statistics, RR with 95% CI and P value).
- 5) IR of subgroups of patients using 5 types of culture media (regardless the method of embryo assessment, descriptive summary statistics and 95% CI)

15 Safety Evaluation

In conformity with protocol, device deficiency will be individually listed.

16 References

No reference at this stage

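### No required assessment supports the week 10–12 ongoing-pregnancy endpoint, the documents conflict on follow-up after week 8, and no denominator or unknown-status rule is given

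*Protocol*

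**What the plan says.** **Endpoints.** Protocol 7.4.2 lists "Ongoing pregnancy rate (assessed by ultrasonography at weeks 10 to12" and "Spontaneous miscarriage (communicated during medical appointment or by telephone contact" among the secondary endpoints. Protocol 4.2 and SAP 5.2 repeat both. Protocol 6.1 names ongoing pregnancy but does not define it, and describes miscarriage this way: "Spontaneous miscarriage rate as a desired follow-up endpoint".

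**Data after week 8.** Protocol 6.3.9 provides a form for later scans and says "The collection of this data is optional, however encouraged"; SAP 5.4.10 and 19.2.7 keep the optional label. Protocol 6.3.8 has pregnancy outcome obtained by visit, telephone or HFEA database on a Post-Pregnancy Follow-up eCRF, without a week. Protocol 5.1 also says pregnancy outcomes are to be collected, then adds that "additional collection of outcomes like spontaneous miscarriage is not being considered in the timeline for completion". In the safety section, 6.4.1.2 states: "There is no pregnancy follow-up planned in the frame of this study".

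**Closure.** Protocol Section 12 defines completion as the point "when all subjects enrolled have completed the 5-8 weeks Ultrasound or Clinical Pregnancy data collection requirements" or have already exited, and also asks for eCRFs and queries to be complete.

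**Analysis.** SAP 14.4 and 14.5 give an estimate and 95% CI for each secondary rate in EMG, MG, EC and ENC, on the ITT and KID selections. SAP 14.6 lists, as analyses that could be run, "IR, CPR, OPR and SMR of the two treatment groups for subgroups of patients with ET on D3 and D5/6", with risk ratios and P values, and the same by age. Protocol 7.6.1 rules out imputation.

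**The concern.** An endpoint defined by a scan in a fixed window needs that scan, or an accepted substitute, for every woman who could still be pregnant. Here the scan is optional and the substitute contact has no date. A telephone outcome need not establish status at weeks 10–12, and the plan does not say whether it counts.

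Women with a negative test or no heartbeat at weeks 5–8 leave the trial with a known result (6.3.6, 6.3.7). Unknown status therefore falls only on women with a heartbeat at that scan, the group that determines both rates. The trial is unblinded (7.13), later scans depend on the site, and the one database named serves a single country (UK) of eight. Capture could differ by site, arm and outcome, and the planned intervals would not show it.

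**Working it through.** **1. The passages side by side**

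| Later follow-up reads as planned | Later follow-up reads as not secured |
|---|---|
| 5.1: pregnancy outcomes go on the eCRF for women pregnant at the week 5–8 visit | 5.1: miscarriage collection is left out of the completion timeline |
| 6.3.8: outcome obtained by visit, telephone or database | Section 6 (opening): final outcome included only where available |
| 7.12: data collection extends to miscarriage and live birth | 6.1: miscarriage is only a desired endpoint |
| Section 12: eCRFs must be complete before closure | Section 12: the clinical trigger is the week 5–8 scan; 6.4.1.2: no pregnancy follow-up planned |

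SAP Section 17 has outcome codes for miscarriage, pregnancy lost and ongoing pregnancy, but none is tied to weeks 10–12.

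**2. The plan's own precision figures**

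Protocol 7.2 tabulates the distance to the 95% limit, h = 1.96 × √(p(1−p)/n), with n = subjects. At p = 0.40, n = 500 gives 4.29 (stated 4.3) and n = 1,000 gives 3.04 (stated 3.0). All ten entries reproduce to one decimal. The table concerns implantation; nothing is sized for ongoing pregnancy or miscarriage. I use the same formula as a yardstick.

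**3. Ongoing pregnancy: worst-case range**

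The documents give no rates. Assumed: clinical pregnancy rate c = 30–45%, later loss 5–15%, all women in the arm as denominator. Let m be the share of clinical pregnancies without week 10–12 status. Counting those women first as all ongoing and then as all lost moves the rate by c × m. This equals the half-width h when m = h / c.

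- c = 0.40, loss 10%: true rate 0.40 × 0.90 = 36.0%. For n = 1,000, h = 2.98 points and m = 2.98/40 = 7.4%. For n = 500, h = 4.21 points and m = 4.21/40 = 10.5%.
- Over the whole assumed range, m runs from 6.7% to 9.3% (n = 1,000) and from 9.5% to 13.2% (n = 500).
- At c = 0.40, 20% missing gives an 8-point range and 40% missing gives 16 points.

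**4. Ongoing pregnancy: dropping unknowns**

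Negative results are always known, so removing women of unknown status lowers the rate even when capture is not selective. With c = 0.40, loss 10% and 80% capture of both outcomes: (0.40 × 0.90 × 0.80) / (0.60 + 0.40 × 0.80) = 0.288/0.92 = 31.3%, against a true 36.0%.

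**5. Miscarriage per clinical pregnancy**

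Let L be the true loss and a, b the shares of losses and of ongoing pregnancies captured. The observed rate is La / (La + (1−L)b). Assume L = 10%.

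- a = 60%, b = 90%: 0.06/(0.06 + 0.81) = 6.9%
- a = 90%, b = 60%: 0.09/(0.09 + 0.54) = 14.3%
- a = b = 80%: 0.08/(0.08 + 0.72) = 10.0%, no bias

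**6. Calendar**

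Synopsis: last patient in 31 October 2016, last visit 31 December 2016, 61 days. Assuming entry on Day 1 after retrieval (2w1d, 15 days), the last entrant is at 15 + 61 = 76 days, or 10w6d. She reaches 12w6d (90 days) on 14 January 2017, 14 days after the stated last visit. The 7.9 calendar (31 January to 31 March 2016, 60 days) gives 10w5d.

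**The case against.** A reader might infer that everything after week 8 is optional, that the trial closes at the week 5–8 scan, and that both rates will therefore rest on selective data. The documents do not support that.

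- Only the scan is optional. Protocol 5.1, 6.3.8 and 7.12 word the collection of outcome as planned, and SAP 5.4.9, 17 and 19.2.10 provide for pregnancy outcome, outcome codes and dates up to live birth. Miscarriage has a source that does not depend on the optional scan.
- Section 12 also requires completed eCRFs, and the follow-up form is an eCRF. Whether closure waits for it is unclear; that it does not wait is not established.
- The sentence in 6.4.1.2 defines the safety reporting period. It clashes in wording with 5.1 and 6.3.8 but does not show that efficacy outcomes go uncollected.
- The trial is exploratory, SAP 14.1 calls it descriptive, and the subgroup P values are only possible analyses. The CIs are firm.
- No missing-data rate is given, and equal capture leaves the miscarriage rate unbiased. Bias is a risk, not a certainty.
- The calendar effect is small. Entrants in the last 14 of 490 enrolment days (29 June 2015 to 31 October 2016), or 2.9% if accrual is even, would not reach 12w6d by the stated last visit.

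All of this stands and narrows the point. It does not supply a required week 10–12 assessment, a time point for the follow-up, or a rule for unknown status.

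**Conclusion.** The point holds in a limited form. It is firm for ongoing pregnancy: the endpoint is defined by a scan that nobody is required to do or record, the alternative contact is undated, and intervals are planned with neither a denominator nor a rule for unknown status. For miscarriage the data source exists. The defect there is the conflict over whether it is secured, plus the same missing denominator and rule.

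The size rests on assumed rates only. Unknown status in roughly 7–9% (n = 1,000) or 10–13% (n = 500) of clinical pregnancies is enough for the worst-case range in the ongoing rate to match the full-data half-width. A true 10% miscarriage rate could read anywhere from 6.9% to 14.3% under the unequal capture shown, and 10% under equal capture. The documents do not show that such gaps will occur; they do not prevent them either.

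**What to change.** 1. Make dated pregnancy status at weeks 10–12 (ongoing, lost, unknown) a required field of the existing Post-Pregnancy Follow-up eCRF for every woman with a heartbeat at the week 5–8 scan, using the contact routes already in 6.3.8. Word the endpoint as status at weeks 10–12 by scan or documented contact.
2. State that closure and database lock wait until the last such woman has passed week 12. Reconcile Protocol 5.1, Section 6, 6.1, 6.3.8, 6.4.1.2, 7.12 and Section 12.
3. In the SAP, count test-negative and scan-negative women as not ongoing. Give one denominator for miscarriage and take its numerator from the same women; if losses seen at the week 5–8 scan count, the women in whom they were seen belong in the denominator. Report the number with unknown status by arm, with best- and worst-case bounds.

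If item 1 is not adopted, report both rates as incomplete descriptive data and drop their optional subgroup P values.

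**Cost.** One eCRF field, wording changes, and a lock about two weeks beyond the synopsis last visit (under the Day 1 entry assumption). No scan is added. The timed contact would apply to about 450–675 of 1,500 women (0.30 × 1,500 to 0.45 × 1,500, at the assumed clinical pregnancy rates).

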6.4 Assessment of Safety

Safety of Eeva will be evaluated by assessment of device deficiency only.

An adverse event or a serious adverse event, whether or not related to the investigational medical device Eeva, in subjects participating to the study is not applicable. In addition, given the design of this study and the reporting period for safety surveillance, assessment of serious adverse device effects in offspring of subjects participating in the trial is not applicable (see definitions).

6.4.1 Definitions

6.4.1.1 Specific Definitions

As per the European Guidelines on medical devices (MEDDEV 2.7/3), dated December 2010.

An **Adverse Event (AE)** is any untoward medical occurrence, unintended disease or injury or any untoward clinical signs (including an abnormal laboratory finding) in subjects, users or other persons whether or not related to the investigational medical device.

A **device deficiency** is an “Inadequacy of a medical device related to its identity, quality, durability, reliability, safety or performance, such as malfunction, misuse or use error and inadequate labeling.

Device Malfunction: A failure of a device to perform in accordance with its intended purpose when used in accordance with the manufacturer’s instructions.

Use Error: Act or omission of an act that has a different result to that intended by the manufacturer or expected by the operator.

A **Serious Adverse Device Effect** is “an adverse device effects that has resulted in any of the consequences characteristics of a serious adverse event”.

A **Serious Adverse Event (SAE)** is an adverse event that:

(In the consented subjects)

- a) Led to a death,
- b) Led to a serious deterioration in health that either:
 - 1) Resulted in a life-threatening illness or injury, or
 - 2) Resulted in a permanent of a body structure or a body function, or
 - 3) Required in-patient hospitalization or prolongation of existing hospitalization, or
 - 4) Resulted in medical or surgical intervention to prevent life threatening illness or injury or permanent impairment to a body structure or a body function.

In the offspring of consented subjects:

- 5) Led to fetal distress, fetal death or congenital abnormality or birth defect

6.4.1.2 Definition of the reporting period for safety surveillance

The reporting period for safety surveillance begins when the subject is included into the trial (date of first signature of informed consent) and continues after ET until achievement of implantation and (confirmation of) pregnancy. There is no pregnancy follow-up planned in the frame of this study.

6.4.2 Device Deficiency

6.4.2.1 Methods of recording Device Deficiencies

Any feedback in regard to Eeva will be collected on the **Device Incident** eCRF.

Feedback may consist of any alleged deficiency related to the physical characteristics, identity, quality, durability, reliability, effectiveness, or performance of Eeva.

PPD [REDACTED]. Engineering and Quality will investigate device malfunctions/deficiencies and perform an evaluation to determine and document the root cause of any device deficiency. Reports will be filed in the Eeva trial project file and/or in document control. Refer to Section 6.4.1.1. for additional information and definition.

6.4.2.2 Reporting of Device Deficiencies

Investigators are responsible for reporting to Merck KGaA via the eCRF device deficiencies that may affect the assessment process of the embryos during the course of embryo culture through trial completion.

An assessment of the device deficiency by the investigator is not mandatory.

PPD [REDACTED]. is responsible for reporting of device deficiencies to NCA (National Competent Authorities) according to applicable legal post-marketing reporting obligations for medical devices.

6.5 Reporting after the defined reporting period for safety surveillance

Beyond the defined reporting period of this study, it is the responsibility of the investigators informed of any serious abnormal pregnancy outcome in subjects who participated to this study, including of any congenital anomalies in the offspring of these subjects, to spontaneously reported the serious adverse events either directly to the marketing holder of EEVA or to their local regulatory health authorities, if necessary, as required by the local ADR reporting guidelines.

7 Data Analysis and Statistics

7.1 Predetermination of Sample Size

7.2 Sample Size

This is an exploratory trial to generate hypotheses for future confirmatory clinical trials.

It is planned to enroll 1000 subjects in the group of subjects with embryo transfers using Eeva scores plus morphology grading and 500 subjects into the control group of subjects with embryo transfers using morphology grading only. Enrollment is non-competitive, each center selected to participate in the study is expected to enroll a minimum number of patients to be defined at site start-up.

Based on this number of subject's precise estimates of the primary endpoint, the rate of implantation for Day 3/5 embryo transfers, is possible.

The following table shows for different implantation rates the distance from the rate (proportion) to the limit of a 95% confidence interval.

Implantation rate	Distance to limit of 95% CI	
	500 subjects	1000 subjects
25%	3.8	2.7
30%	4.0	2.8
35%	4.2	3.0
40%	4.3	3.0
45%	4.4	3.1

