4.1 Primary

The primary objective of the trial is to compare the rate of implantation for Day 3/5 embryo transfers using Eeva scores plus morphology grading versus Day 3/5 embryo transfers using morphology grading only. Implantation rates are calculated by dividing the number of gestational sacs with fetal heart beat identified by ultrasonography at weeks 5 to 8 by the number of embryos transferred on Days 3 or 5.

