7.3 Randomization

Subjects will be assigned to the group of subjects with embryo transfers using Eeva scores plus morphology grading and to group of subjects with embryo transfers using morphology grading only by randomization. A permuted block randomization with fixed block size and allocation ratio of 2:1 will be used. Further details of the procedure will be described in the EDC related Manuals.

An allocation ratio of 2:1 is used since this is an explorative trial. The main objective is to collect data of first experience with the EEVA Time Lapse system. To generate hypotheses in

comparison to the ‘morphology grading only’ group comparable data of the morphology grading only need to be collected.

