7.4 Endpoints

7.4.1 Primary Endpoint(s)

The primary endpoint is the Implantation Rate from embryo transfers performed on day 3 or 5. The crude estimate of the implantation for each embryo assessment method (Eeva scores plus morphology grading, morphology grading only) will be calculated as the ratio of the total fetal sacs identified by ultrasonography at weeks 5 to 8 and the number of embryos transferred.

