14.1 Primary analysis

Implantation rate will be analyzed with two definitions

First definition: The IR (at embryo level) corresponding to a group of patients is calculated as the ratio of the total fetal sacs (nFS) identified by ultrasonography at weeks 5 to 8 divided by the number of embryos transferred (nET), thus $IR = nFS/nET$.

Alternative Definition of Implantation Rate: The previous (and usual) calculation of IR as mentioned in the protocol ($IR = nFS/nET$) has problems, in particular the implanted embryos are not independent. The international definition used by WHO in particular (see for instance <http://www.advancedfertility.com/ivf.htm>) is: The alternative definition IR^* at women level is $IR_w = nFS_w/nET_w$ and $IR^* = (1/n) \cdot \sum_{w=1,n} IR_w$.

Note: The two definitions IR and IR^* coincide in some cases, in particular for elective Single Embryo transfer eSET (where only one embryo is transferred) or when KID sample is used, but in the general case (ITT sample for instance, IR and IR^* will be different).

The point estimate and 95% CI of IR and IR^* will be calculated in both groups EMG and MG for the ITT selection. No inferential comparison will be conducted between these two groups (as this study is purely descriptive).

The following sections are considered as secondary analyses.

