Psupp	Protein Supplement	C	4	1= None used, 2 = SPS, 3 = HAS, 4 = SSS, 5 = Other
Negg	N of retrieved eggs	I	6.1	
eggGV	Egg type GV	B		
eggMI	Egg type MI	B		
eggMII	Egg type MII	B		
eggOt	Egg type Other	B		
Trf	Was a transfer attempted ?	B		
Nte	N of transferred Embryos	I	4.1	
Usg	Ultra sound guided	B		1=Yes 2=No
Cat1	Catheter Typ Mucous	B		
Cat2	Catheter Typ Blood	B		
Cat3	Catheter Typ retained embryos	B		
Cat4	Catheter Typ N/A	B		
Grading	Procedure Grading	C	4	1= Easy 2= Difficult
Pdg	Embryo assessed by PGD/PGS	C	4	1=Yes 2=No
Euploid	Euploid transferred ?	B	4	
LPS	Luteal Phase support	B		1=Yes 2=No
DelMet	Delivery Method	C		1= Crinone 2=Endometrin 3=Other Vaginal 4=Intramuscular 5=Other
Test1	Post Transfer test 1	B		1= Urine 2=Blood
Test1r	Post Transfer test 1 result	B		1= Positive 2= Negative
Test2	Post Transfer test 2	B		1= Urine 2=Blood
Test2r	Post Transfer test 2 result	B		1= Positive 2= Negative

US1	Ultra Sound result	B		1= Positive 2= Negative
Nsac	N of gestational Sacs	I	4:1	
Nhbt	N of Heartbeats	I	4:1	
Outc	Final outcome further to Ultra Sound	C		1=No pregnancy 2=Biochemical pregnancy 3=Ectopic 4=miscarriage 5= Ongoing
EndPP	Cycle completed on Per Protocol	B		1=yes 2=o
cycleCSt	IF cycle complete : Status	C		1= Ongoing pregnancy 2= Pregnancy came to term 3= Pregnancy lost 4= Failed to conceive 9= therapeutic abortion 10= Other
cycleNst	If cycle non complete : Status	C		0=Normal 1= OHSS risk 2= Embryo transfer cancelled 5= Freeze all 6= Other 7= Imaging discontinued prior to completion 8= Subject requested to be withdrawn 9= Investigator withdrew subject 10= Subject was lost to follow-up 11= Subject was noncompliant

18 Table description: principles of reporting

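### The precision table behind 1000 + 500 subjects counts randomised subjects, while the primary endpoint it describes counts embryos transferred, so its half-widths fit that endpoint only in special cases

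*Protocol*

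**What the plan says.** Protocol 7.2 plans to "enroll 1000 subjects in the group of subjects with embryo transfers using Eeva scores plus morphology grading and 500 subjects into the control group". It gives no effect size, power or margin. The support offered for these numbers is that "precise estimates of the primary endpoint, the rate of implantation for Day 3/5 embryo transfers, is possible", followed by a table of "the distance from the rate (proportion) to the limit of a 95% confidence interval" for rates from 25% to 45%, in columns headed by 500 and 1000 subjects.

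The endpoint has a different denominator. Protocol 4.1 divides "by the number of embryos transferred on Days 3 or 5", and Protocol 7.4.1 has the rate "calculated as the ratio of the total fetal sacs identified by ultrasonography at weeks 5 to 8 and the number of embryos transferred". SAP 14.1 keeps this as its first definition: "The IR (at embryo level) corresponding to a group of patients is calculated as the ratio of the total fetal sacs", divided by embryos transferred. The same section concedes that implanted embryos are not independent. It adds a second rate, IR*, which averages each woman's own sacs-to-embryos fraction, and it plans 95% intervals for both rates in each arm.

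SAP 8.3 provides for transfers of one, two or three embryos. The codes for incomplete cycles in SAP section 17 include "1= OHSS risk 2= Embryo transfer cancelled 5= Freeze all", so some randomised women may have no transfer. SAP section 6 adds no calculation: it refers back to Protocol 5.3, which is the population section.

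**The concern.** The table is presented as the precision of the primary endpoint but appears to be computed on another unit. A woman with two embryos transferred adds two correlated units to the denominator; a woman with no transfer adds none. The table counts each of them as one independent yes/no outcome.

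In a trial with no power claim, precision is the whole case for the sample size. Interval width is also part of what the trial is meant to deliver: Protocol 5.2 wants realistic confidence intervals from which a later randomised trial can be planned. Someone planning that trial from the 7.2 table would be reading half-widths for a different quantity.

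**Working it through.** **Inputs from the documents.** n = 500 and 1000 subjects (Protocol 7.2; 2:1 allocation in 7.3); rates p of 25% to 45%; 95% intervals; denominator embryos transferred (Protocol 4.1 and 7.4.1, SAP 14.1).

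**Inputs the documents do not give, so assumed below.** The share of randomised women with a transfer, f; the distribution of embryos per transfer, m; the within-woman correlation, ICC.

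**Step 1: reproduce the table.** Half-width = 100 × 1.96 × √(p(1−p)/n).

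| Rate | 500: computed | 500: stated | 1000: computed | 1000: stated |
|---|---|---|---|---|
| 25% | 3.795 | 3.8 | 2.684 | 2.7 |
| 30% | 4.017 | 4.0 | 2.840 | 2.8 |
| 35% | 4.181 | 4.2 | 2.956 | 3.0 |
| 40% | 4.294 | 4.3 | 3.036 | 3.0 |
| 45% | 4.361 | 4.4 | 3.083 | 3.1 |

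All ten entries match. Taking 1.5 embryos per subject as n would give 3.10 and 2.19 at 25%, which does not match. The unit is the subject.

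**Step 2: half-width for the embryo-level rate.** With clustering,

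half-width = 100 × 1.96 × √( p(1−p) × D / (f × n × E[m]) ), where D = 1 + (E[m²]/E[m] − 1) × ICC.

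This is the Step 1 figure multiplied by √(D / (f × E[m])). It assumes an interval that allows for the clustering; SAP 14.1 names no interval method.

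**Step 3: numbers at 35%** (table: 4.18 / 2.96 before rounding). A mean of 1.5 is taken as half single and half double transfers, so E[m²] = 2.5 and E[m²]/E[m] − 1 = 0.667.

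| f | E[m] | ICC | D | Multiplier | 500 | 1000 |
|---|---|---|---|---|---|---|
| 1.0 | 1 | any | 1 | 1.000 | 4.18 | 2.96 |
| 1.0 | 2 (all double) | 1 | 2 | 1.000 | 4.18 | 2.96 |
| 1.0 | 1.5 | 0.2 | 1.133 | 0.869 | 3.63 | 2.57 |
| 1.0 | 1.5 | 0.4 | 1.267 | 0.919 | 3.84 | 2.72 |
| 1.0 | 2 | 0.2 | 1.2 | 0.775 | 3.24 | 2.29 |
| 1.0 | 2 | 0.4 | 1.4 | 0.837 | 3.50 | 2.47 |
| 0.9 | 1 | any | 1 | 1.054 | 4.41 | 3.12 |
| 0.8 | 1 | any | 1 | 1.118 | 4.67 | 3.31 |
| 0.9 | 1.5 | 0.2 | 1.133 | 0.916 | 3.83 | 2.71 |
| 0.8 | 1.5 | 0.2 | 1.133 | 0.972 | 4.06 | 2.87 |

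The table is right when D = f × E[m]. The first two rows show the structural cases: one embryo in every woman, or a constant number per woman with complete correlation and everyone transferred. Other combinations reach equality by coincidence: f = 0.8, E[m] = 1.5 and ICC = 0.3 give 1.2 / (0.8 × 1.5) = 1.

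**Step 4: the woman-level rate IR\*.** Here the woman is the unit, but her outcome is a fraction. A variable lying between 0 and 1 with mean p has variance at most p(1−p), so the half-width is at most 100 × 1.96 × √(p(1−p)/n), with n the number of women who had a transfer. On that reading of n, the table is an approximate upper bound for IR*.

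**Step 5: the difference between arms, on the table's own assumptions.** 100 × 1.96 × √(0.35 × 0.65 × (1/500 + 1/1000)) = 5.12 points.

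**The case against.** The arithmetic in the table is correct; what is missing is a statement of the assumption under it. For IR*, one of the two rates in the SAP's primary analysis, the woman is the right unit and the table is roughly an upper bound. If every woman has a transfer and correlation is low to moderate, the table is conservative for the embryo-level rate too.

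The optimistic side depends on women without a transfer, and no document gives their share. The exit codes show that non-transfer can happen, not that it is common. The eligibility rules work against it: at least four normally fertilised eggs are required, planned freeze-all cycles are excluded, and enrolment is settled on day 1 after egg collection. The trial is exploratory, and under the labelled assumptions above the 35% figure moves by less than one point in the 500-subject arm.

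All of this stands, and it limits the size of the point. It does not remove the point, because 7.2 says the table describes the primary endpoint, that endpoint is per embryo in every protocol definition, and neither document states the condition under which the two agree.

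A reader might also infer that the plan wrongly omits the precision of the between-arm difference. Protocol 4.1 and 7.6.2 do compare the arms, but SAP 14.1 makes the primary output per-arm intervals with no inferential comparison. The difference is therefore a useful addition rather than a required correction.

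**Conclusion.** The point holds. The only stated justification for 1000 + 500 subjects is computed per randomised subject, while the endpoint it names is per embryo transferred, and the two agree only in special cases.

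At 35%, against a stated 4.2 / 3.0:

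- About 3.2–3.8 / 2.3–2.7 if all women are transferred, with a mean of 1.5 to 2 embryos and correlation 0.2 to 0.4. That is 8% to 23% narrower, so the table is conservative.
- About 4.4–4.7 / 3.1–3.3 with single transfer and 10–20% of women untransferred. That is 5% to 12% wider, so the table is optimistic.

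Both sets rest on assumed values of f, m and ICC. Three stronger readings are tempting but unsupported. The documents do not show that 1500 is too few. They do not show that the table overstates precision, since the direction depends on quantities they do not give. Nor is it true that the table holds only with exactly one embryo per woman, as the all-double row with complete correlation shows.

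**What to change.** Restate the 7.2 table for the endpoint as defined. Give the assumed transfer share f, the distribution of embryos per transfer and the within-woman correlation, ideally as a small range, and compute the IR half-width in percentage points as 100 × 1.96 × √( p(1−p) × [1 + (E[m²]/E[m] − 1) × ICC] / (f × n × E[m]) ). The E[m²]/E[m] term matters because transfer numbers are mixed: at E[m] = 1.5 and ICC = 0.4, the equal-cluster form 1 + (E[m] − 1) × ICC = 1.2 would give 3.74 for 500 subjects instead of 3.84.

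Add a matching line for IR* with n equal to the number of women with a transfer, and point SAP section 6 to the revised text. Keep the sample size unchanged. Optionally add the 1000:500 half-width for the difference (5.1 points at 35% on the present table's assumptions), labelled as descriptive.

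The cost is a text change with no extra patients or data. Some stated figures may become slightly less favourable.
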